Background: Oral lichen planus (OLP) is a chronic inflammatory mucocutaneous disease with uncertain etiology. It may appear as bilateral white striations, papules, plaques, erythema, erosions and blisters on the buccal mucosa, tongue and gingiva.

Conventionally, corticosteroid treatments are used as a treatment in Erosive OLP. As an alternative method to steroid therapies Diode lasers were introduced for the symptomatic relief of pain and burning sensation with no adverse effects.

Study objective: the objective of the study is to compare the effect of topical corticosteroid and 980nm Diode Laser in the treatment of erosive OLP.

Materials and Methods: This study will be conducted on 44 patients histologically diagnosed erosive OLP. Patients will be divided into two groups: Group I: 22 patients will be given conventional treatment (topical corticosteroid), Group II: 22 patients will be treated with 980nm Diode Laser. The pain score, clinical and biochemical evaluation will be done at the beginning of the treatment, 6 weeks and 12 weeks after treatment. The evaluation will be done using Visual Analogue Scale (VAS) for pain assessment, the criteria scale described and modified by Thongprasom et al 2003 for clinical assessment, and oxidative stress biomarker analysis for the biochemical evaluation.

Results: The data obtained will be collected and statistically analyzed.

Keywords: Oral lichen planus, 980 nm Diode Laser, topical steroid therapy.

Introduction

Oral lichen planus (OLP) is a chronic inflammatory mucocutaneous disease, which affects the skin, nails, hair and mucous membranes, recognized in 1866. ¹ It affects 1%–2% of the population at middle age, with a female predominance. OLP etiology is unknown but evidence suggests that this disease is an immune-mediated process involving cytotoxic T cells as well as the release of a diverse array of proinflammatory cytokines that lead to the apoptosis of epithelial cells. ²

Although the immunological system plays a substantial role in OLP, other factors may be also involved, such as psychological stress, drug intake, anxiety and some systemic diseases, including hepatitis C virus infection, hypertension, diabetes, and graft-vs-host disease. However, the precise role of most of these conditions in OLP remains unclear.³

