However, the efficacy of laser in OLP treatment remains uncertain. Some studies have shown that conventional therapy with topical corticoids showed better control of OLP pain and size when compared to lasers. ¹⁴ On the other hand, other studies have demonstrated comparable outcomes for patients treated with both laser and corticoids. However, these studies used different laser parameters and no protocol for laser could be established. ^{15,16}

These different results of laser therapy may need further investigations to resolve the conflict and to assess the effectiveness of LLLT in treatment of OLP.

The purpose of this study is to evaluate the effectiveness of 980nm Diode Laser in the treatment of erosive OLP in relation to conventional corticosteroids.

The null hypothesis of this research is that there will be no statistically significant difference among the test group treated by 980nm Diode Laser and the control group treated by conventional therapy.

AIM OF THE STUDY

The aim of the study is to evaluate the effect of 980nm Diode Laser in the treatment of erosive OLP compared with conventional topical corticosteroid therapy.

Primary Objective

To evaluate clinically on Visual Analogue Scale (VAS) the ability of 980nm Diode Laser to control pain compared with topical corticosteroid.

Secondary Objective

To test the clinical improvement of OLP according to Thongprasom et al 2003 scoring system and to evaluate the oxidative stress in saliva biochemically.

FLOW CHART STUDY DESIGN

PLAN OF THE STUDY

Material and Methods

I. Material

i. Study design and setting:

This randomized, controlled, clinical trial will be conducted on 44 patients of both sexes who complain from erosive OLP. They will be selected from the outpatient clinic of Department of oral medicine, Faculty of dentistry.

Patients will be given a detailed explanation of the study and will sign an informed consent form according to the guidelines of the Ethical Committee of the Faculty of Dentistry, Alexandria University. They will be treated according to the principles of the modified Helsinki's code for human clinical studies (2013).¹⁷

Inclusion Criteria

- Patient histologically diagnosed with erosive OLP based on WHO modified criteria 2003. ¹⁸
- 2. Patients 30-70 years of age.
- 3. Presence of painful erosive OLP lesions diagnosed by biopsy.¹⁸

Exclusion Criteria

- 1. Pregnant or breast-feeding women.¹⁸
- 2. Patients currently treated for cancer with Chemotherapy or Radiotherapy.¹⁵

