- 3. Patient currently on Corticosteroid therapy or had been on treatment on the past 3 months.¹⁸

- 4. Those who had used Anti-inflammatory drugs topical or systemic in the last month.²
- 5. Those who reported use of drugs related to Oral Lichenoid Lesions.²
- 6. Presence of Amalgam restorations near the OLP lesions.²⁰
- 7. Those with description of dysplasia in histopathological examination. ²⁰
- 8. Patients suffering from any uncontrolled systemic diseases (such as diabetes, cardiovascular, liver disorder, renal dysfunction)²⁰
- 9. Patients with findings of any physical or mental abnormality which would interfere with or be affected by the study procedure. ²
- 10.Patients with skin lesion.

ii. Sample size calculation:

Sample size will be estimated assuming confidence level = 95% and study power = 80%. The mean (SD) reported pain scores measured by the Visual Analogue Scale after 3 months for the laser group was 0.79 (1.23) and for the steroid group was 2.81 (2.84). The minimum sample size was calculated to be 20 patients, increased to 22 patients per group to make up for possible loss to follow up.

The total sample size = number of groups \times number per group= 2 X 22= 44 patients.

Sample size was based on Rosner's method calculated by G power 3.0.10. 21, 22, 26

II. Methods

Randomized Controlled Clinical Study

The purpose and nature of the study will be explained for the selected 44 patients and an informed consent will be obtained from patients who agree to participate in this study prior to any procedure.

An incisional biopsy will be performed under local anesthesia from the lesion to exclude dysplasia and cancer.

Grouping and Randomization

The selected patients will be randomly assigned to the following groups:

Group I (Control group)

22 patients will be given topical corticosteroid 0.1% topical triamcinolone acetonide preparation (0.1% triamcinolone acetonide orabase, Kenacort-A Orabase Pomad, DEVA HOLDING A.Ş, Istanbul, Turkey) three times daily for 4 weeks.

The application should be in one direction with no food or fluid after administration for a minimum of 1 hour post application. Also, patient will be applying miconazol oral gel once daily to avoid superimposed fungal infection.²⁰

Group II (Study group)

22 patients will be subjected to laser therapy by the 980 nm diode laser (MEDENCY ,PRIMO – Vicenza Italy) for photobiomodulation (PBM) and the treatment will be continued up to 10 sessions (2 sessions per week).

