A Fiber Tip with a diameter of $400\mu m$ will be used. The output power will be 300 mW and the average power density about 1 W/cm². A "spot" technique will be used, with a slight overlapping in order to evenly distribute energy covering all the mucosal lesions and also the peri-lesional tissues up to 0.5 cm.

Each session will be performed delivering a fluence of 4 J/cm2 per lesion, and the probe will be held perpendicularly at a distance of about 2 mm. The time of delivery per point of application is approximately 4 Sec in continuous wave with 2 sessions weekly. After each laser session, a cold diet will be recommended. ^{20,22}

Allocation concealment

Allocation of cases will be via block randomization method using a computer generated random sequence into 2 groups of equal numbers (N=22 patient/ group).²⁷

Allocation will be informed by a trial independent individual. The participant allocation will be kept in opaque, sealed envelopes and arranged sequentially by a dental assistant, who will not be involved in the study.

Each envelop will be opened after completing the oral examination and right before the application of the intervention.

A) After biopsy and before treatment:

1. Detailed medical and dental history will be obtained from the selected patients.

2. Thorough intraoral examination will be performed to determine the need for scaling and treatment of any source of irritation.

3. Oral hygiene instructions will be carried out to all patients.

4. Adequate hydration will be advised.

5. Every group of patients will be given their treatment protocol.

B) During and after treatment:

Clinical Evaluation:

All patients will be clinically and biochemically evaluated before treatment, after 6 and 12 weeks with following criteria:

1- Subjective assessment

Discomfort and pain severity will be reported by each patient using Visual Analogue Scale (VAS). The VAS consisted of a 10-cm horizontal line marked 0 (=

no pain) to 10 (= most severe pain ever experienced). Patients will be requested to mark the scale at each visit, before and after treatment for each group. Complete resolution of the symptoms (no symptoms) will be defined as the absence of any discomfort, corresponding to a zero VAS score.

The stability of the results in the follow-up period will be also described. ^{20, 22}

2- Objective assessment

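### Does the trial need its primary visit written into the null hypothesis and Primary Objective, given VAS at 6 and 12 weeks and a sample size based on 3 months?

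*Protocol*

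**What the plan says.** The null hypothesis stands at the end of the Introduction as a general sentence: "The null hypothesis of this research is that there will be no statistically significant difference among the test group treated by 980nm Diode Laser", as compared with the group on conventional therapy. It carries no outcome and no time.

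The Primary Objective reads: "To evaluate clinically on Visual Analogue Scale (VAS) the ability of 980nm Diode Laser to control pain compared with topical corticosteroid". It fixes the outcome and the two groups, but not the visit. The Secondary Objective takes the clinical score and the salivary oxidative-stress markers.

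The Sample size calculation uses "reported pain scores measured by the Visual Analogue Scale after 3 months": mean 0.79 (SD 1.23) for laser and 2.81 (SD 2.84) for steroid, at 95% confidence and 80% power. It arrives at 20 per group, raised to 22 for loss to follow-up.

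The visits are described twice. Under Clinical Evaluation: "All patients will be clinically and biochemically evaluated before treatment, after 6 and 12 weeks". In the abstract, evaluation takes place "at the beginning of the treatment, 6 weeks and 12 weeks after treatment". The Subjective assessment section adds "Patients will be requested to mark the scale at each visit, before and after treatment for each group", and then "The stability of the results in the follow-up period will be also described".

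Treatment lasts 4 weeks in Group I. In Group II it runs to at most 10 sessions at two per week.

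**The concern.** A primary comparison needs an outcome, a population contrast and a time. Here the hypothesis gives only the contrast, the objective gives outcome and contrast, and the time appears only as an input to the sample size. With two post-baseline VAS visits, a reader could fear that whichever visit favours laser will be reported as the primary result. Choosing the visit after seeing the data would push the false-positive rate above the 5% that the 95% confidence level implies.

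Two further details feed the worry. The sentence on stability in the follow-up period could be read as making the earlier visit the result and the later one its follow-up. In addition, the abstract can be read as counting weeks from the end of treatment, whereas Clinical Evaluation can be read as counting from its start. Treatment length may differ between groups, so the two readings place the last visit differently.

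**Working it through.** **1. Reproduce the stated sample size.** Inputs are from the Sample size calculation: means 0.79 and 2.81, SDs 1.23 and 2.84, 95% confidence, 80% power. Two-sided testing is assumed, since sidedness is not stated.

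- Difference = 2.81 − 0.79 = 2.02.
- Pooled SD = √((1.23² + 2.84²)/2) = 2.188.
- Standardised difference = 2.02/2.188 = 0.923.
- The two-sample t test at two-sided 5% needs 19.43 per group, rounded up to 20. This is the protocol's figure.
- One-sided testing would need 15.2, rounded up to 16, which does not match.

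| Per group | Power, two-sided 5% t test |
|---|---|
| 19 | 79.1% |
| 20 | 81.2% |
| 22 | 84.9% |

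The stated size is therefore what one unadjusted two-sided comparison of mean VAS at 3 months requires.

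**2. Which visit does that comparison correspond to?** Three months is about 52/4 = 13 weeks. The scheduled post-baseline visits are at 6 and 12 weeks. If the 3 months and the visit weeks are counted from the same origin, 12 weeks is one week away and 6 weeks is seven. No mean or SD is given for 6 weeks, so the protocol contains no sizing for that visit.

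**3. Do the statements conflict?**

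| Place | Outcome | Groups | Time |
|---|---|---|---|
| Null hypothesis | not stated | laser, conventional therapy | not stated |
| Primary Objective | VAS pain | laser, topical corticosteroid | not stated |
| Sample size | VAS pain | laser, steroid | 3 months |

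Each line adds to the one above and none contradicts another. The objective and the sample size agree on outcome and groups, and only the sample size gives a time.

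**4. Size of the feared inflation.** Suppose VAS were tested at 5% at both visits and either could count. With independent tests, the chance of at least one false positive is 1 − 0.95² = 9.75%. For correlated tests it is 1 − P(|Z₁| < 1.96 and |Z₂| < 1.96) under a bivariate normal distribution:

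| Assumed correlation | At least one false positive |
|---|---|
| 0 | 9.8% |
| 0.5 | 9.1% |
| 0.8 | 7.8% |
| 0.9 | 7.0% |

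Both ingredients, the either-visit rule and the correlation, are assumptions that the protocol does not supply. With the single 12-week test the rate stays at 5%.

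**5. Time origin.** Laser treatment lasts at most 10/2 = 5 weeks, and steroid lasts 4. Counted from the start of treatment, the last visit is week 12 in both groups. Counted from the end, it is week 4 + 12 = 16 for steroid and at most 5 + 12 = 17 for laser, the latter only if all 10 sessions are given at the stated pace. With a full laser course the groups differ by one week under the second reading and not at all under the first.

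**The case for a change.** The strongest case for a change is that the visit at which the primary outcome is judged defines what the trial tests, so it belongs in the protocol and should not have to be inferred from a sample-size input. The protocol states a hypothesis, an objective and a sample size, so it has taken the topic on, and two or three sentences would settle it. The choice also bears on size: if both visits were meant to count with a Bonferroni split and the 3-month effect held at each, 24 per group would be needed, and power per test would be 71.9% at 20 and 76.7% at 22.

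Part of this stands. No section shown declares a primary visit, and the two descriptions of the visits are not worded from one origin. The rest carries less weight. Nothing in the protocol says that either visit may count, so neither the Bonferroni figures nor the false-positive range describes this plan. How repeated visits are tested is commonly left to a statistical analysis plan, which may exist and is not shown. The sentence on stability announces a description of results over follow-up and does not rank the visits. The two visit descriptions can be read compatibly, and the looser one under Clinical Evaluation does not contradict the abstract. The study-design flow chart is also missing from the text at hand, so its silence on schedule and origin cannot be assumed.

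**Conclusion.** The concern does not call for a change. It identifies silence about the visit, not a mismatch. VAS is the only primary outcome, the sample size treats that outcome in the same two groups, and its 3-month basis corresponds to the final 12-week visit. An analyst following the protocol would test mean VAS at 12 weeks as primary and report 6 weeks alongside it. That comparison is adequately sized on the protocol's own figures: 81% power at 20 per group and 85% at 22. Writing the visit out would record what is already implied and would leave the design, the sample size and the test unchanged.

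The difference in time origin is loose wording. At most it moves the last visit from week 12 to week 16 or 17, with up to one week between groups if the laser course runs its full length, and no effect on the comparison has been shown.

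This conclusion assumes two-sided testing, which is the only choice of sidedness that reproduces 20, and that the 3 months and the visit weeks share one origin. It would not hold if an analysis plan allowed either visit to count as the primary result, but nothing in the protocol points to that.

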- The size of the lesion and the healing pattern will be monitored. The clinical data will be scored according Thongprasom et al 2003 scoring system. Score 5: white striae with erosive area >1 cm2, Score 4: white striae with erosive area <1 cm2, Score 3: white striae with erythematous area >1 cm2, Score 2: white striae with erythematous area <1 cm2, Score 1: mild white striae only, Score 0: no lesions, normal mucosa. ^{2,24}
- Measurement of Total Oxidative Stress in saliva including Total antioxidant capacity (TAC) and malondialdehyde (MDA). Saliva will be collected before treatment and after 6 and 12 weeks. Saliva will be collected, centrifuged at 30 g for 10 min to evacuate cellular debris and microscopic organisms. The filtered saliva will be stored at -80°C until the time of the biochemical investigation (Tvarijonaviciute, Aznar-Cayuela, Rubio, Ceron, & López-Jornet, 2017). The determination will be measured using the established colorimetric method (Koracevic, Koracevic, Djordjevic, Andrejevic, & Cosic, 2001). Biochemical analysis will be conducted at the Department of Biochemistry, Faculty of Medicine, Alexandria University.²⁵

3- Photographs:

Photographs will be taken at baseline and at the end of the study.

STATISTICAL ANALYSIS

The data will be processed and analysed using Statistical Package for Social Sciences program SPSS software^{*}.

^{*} Armonk, NY: IBM Corp, USA.

ETHICAL CONSIDERATIONS

The clinical part of the study will be performed after the approval of the Research Ethics Committee, Faculty of Dentistry, Alexandria University.

The volunteers will provide written informed consent and the study will be conducted in accordance with the modified Helsinki Declaration of 2013.¹⁴

The patients will receive written consent about the study protocol before agreeing to participate in the study. The patients will have the right to withdraw at any time during the study.

Clinical trials need written informed consent in order to clarify objectives, risks and benefits of the study.

Medical therapy for potential risks will be provided (cortico steroids will be administered in case of severe pain after laser treatment).

DURATION OF THE STUDY

| Months Study activities | 1 | 2 | 3 | 4 | 5 | 6 | 7 | 8 | 9 | 10 | 11 | 12 |
|--|---|---|---|---|---|---|---|---|---|----|--------------|--------------|
| Purchase of materials | ~ | > | | | | | | | | | | |
| Patient selection and Clinical study | | | ~ | ~ | ~ | ~ | ~ | ~ | | | | |

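### The saliva spin of 30 g for 10 minutes can pellet whole cells but leaves most free bacteria of about 1 µm or less in the sample, so it only partly meets its stated purpose

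*Protocol*

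**What the plan says.** The protocol, under 2- Objective assessment in the Methods, has saliva "centrifuged at 30 g for 10 min to evacuate cellular debris and microscopic organisms". It continues: "The filtered saliva will be stored at -80°C until the time of the biochemical investigation". The samples serve TAC and MDA, and the schedule is "Saliva will be collected before treatment and after 6 and 12 weeks". On location it says only this: "Biochemical analysis will be conducted at the Department of Biochemistry, Faculty of Medicine, Alexandria University". A published saliva study is cited for handling and storage.

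TAC and MDA are the biochemical part of the Secondary Objective, which is "to evaluate the oxidative stress in saliva biochemically". The protocol gives no other force, no second spin and no filtration step. It does not give the tube, the volume, the rotor or the person who does the spin.

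**The concern.** A force, a time and a purpose stand in the same sentence, so the setting can be tested against its own aim. 30 g is a gentle spin. It may bring down whole cells, but bacteria are far smaller, and sedimentation speed falls with the square of the diameter. If the spin does not remove them, the step that the protocol requires before the assays is only partly carried out.

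The setting applies to every saliva sample: up to 44 patients × 3 visits = 132. That number counts the samples concerned and says nothing about the size of an effect. A laboratory that follows the text would freeze saliva still holding free bacteria. A laboratory that uses a stronger spin of its own would depart from the protocol, and the reported method would be wrong. The spin cannot be repeated on fresh saliva once the sample is frozen.

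**Working it through.** 30 g is a setting and not a derived figure, so there is nothing to reproduce. The check is whether it can do what the sentence asks.

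**Inputs from the protocol:** relative centrifugal force 30; time 10 min = 600 s.

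**Assumed inputs, not in the protocol:** density excess over the liquid Δρ = 50–100 kg/m³; viscosity η = 0.7–2 mPa·s; liquid column L = 10–40 mm; free single bacteria of diameter d = 0.5–2 µm; 5 µm for yeast-size particles or clumps; 10 µm for a whole cell. Particles are taken as evenly spread at the start and the force as constant along the column.

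**Step 1, distance travelled.** Stokes: travel = d² × Δρ × 9.81 × 30 × 600 / (18 × η).

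For d = 1 µm:
- low end: 10⁻¹² × 50 × 176,580 / (18 × 0.002) = 0.245 mm
- high end: 10⁻¹² × 100 × 176,580 / (18 × 0.0007) = 1.401 mm

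The other sizes scale with d².

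**Step 2, share cleared** = travel / L, capped at 100%. The lowest value pairs the low travel with 40 mm, the highest pairs the high travel with 10 mm.

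| Diameter | Travel (mm) | Share cleared, 10–40 mm column |
|---|---|---|
| 0.5 µm | 0.061–0.350 | 0.15–3.5% |
| 1 µm | 0.245–1.401 | 0.6–14% |
| 2 µm | 0.981–5.606 | 2.5–56% |
| 5 µm | 6.13–35.0 | 15% to all |
| 10 µm | 24.5–140 | 61% to all |

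**Step 3, smallest size fully cleared** = √(L × 18 × η / (Δρ × 9.81 × 30 × 600)). This gives 2.67–6.39 µm for 10 mm, 3.78–9.03 µm for 20 mm and 5.34–12.77 µm for 40 mm.

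**Step 4, sensitivity to the assumptions.**
- A more viscous sample and a longer column (η = 1–3 mPa·s, L = 10–50 mm) give 0.16–0.98 mm for 1 µm. The share cleared is then 0.16/50 = 0.3% to 0.98/10 = 9.8%.
- A sedimentation path of only 5 mm gives 0.245/5 = 4.9% to 1.401/5 = 28% for 1 µm. Most still remain.
- Over the same 5 mm path, 2 µm organisms can be cleared completely at the favourable end, because 5.606 mm exceeds 5 mm.

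The result for about 1 µm and below is therefore stable. The result for 2 µm and above depends on the tube.

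**The case against.** The strongest reply is that the text does not promise a bacteria-free sample. It gives an aim, "to evacuate cellular debris and microscopic organisms", and the spin does remove cells and some of the larger or clumped organisms. The share of salivary organisms that is free and single is not given, and only two inputs of the calculation come from the protocol. This stands: the setting partly meets its purpose, and a flat statement of failure would be too strong.

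A reader might go further in four ways that the documents do not support.

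- **No bacterium can be fully cleared.** That holds only with a column of at least 10 mm and a size of at most 2 µm. A 5 mm path already breaks it for 2 µm, and the protocol gives no path length.
- **All samples are treated alike, so any effect is only noise, equal in both arms.** One setting could give a constant shift, noise or nothing. Equal handling is also not equal organism load: daily miconazole gel is stated for Group I only. Nor does the protocol show that the loads do differ, so a bias cannot be claimed either.
- **30 g is a typing error.** It may be intended, copied, mistyped or damaged when the file was converted to text. The cited procedure is not available here, so this cannot be settled.
- **The word filtered shows a missing filtration step.** After a spin, the natural reading is the supernatant. This is not a separate defect.

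It is also fair to object that no effect on an endpoint has been shown. The documents contain nothing that links residual organisms to TAC or MDA. This keeps the point minor, but it does not make the force fit the purpose.

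**Conclusion.** The point holds as a minor one. At 30 g for 10 minutes, whole cells can pellet, but most free bacteria of about 1 µm or less stay in the supernatant: 0.6–14% of 1 µm bacteria are cleared under the main assumptions, and at most 28% over a 5 mm path. Larger organisms, yeast and clumps clear partly or fully, depending on the tube. The stated setting therefore delivers only part of its stated purpose.

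This rests on Stokes sedimentation and on assumed size, density, viscosity and column height. The size and direction of any effect on TAC and MDA are unknown, and equality between the arms cannot be assumed. The consequence stops at the biochemical part of the secondary objective. The primary outcome, the Thongprasom score and the sample size, which is built on VAS scores, do not depend on the saliva samples.

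**What to change.** Before the first saliva sample, check the 30 g figure against the source protocol file and against the saliva-handling procedure cited in the same paragraph. Do this with whoever performs the spin. The protocol places only the biochemical analysis at the biochemistry department, so that laboratory may not be the one that centrifuges.

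- If the figure is misstated, replace it with the force in that procedure and apply it to all samples, in both arms and at all three visits.
- If 30 g is intended, state that the spin removes cells and debris only and that TAC and MDA are measured in saliva that still contains free bacteria.

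The calculation above shows scale only and should not be used to choose a force. The cost is one figure or one sentence, with no extra patients, visits or samples.
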